4.7.2 Glycemic Endpoints

Similar analysis, as described previously for the BP function endpoints, will be performed for the plasma glucose measurements.

The number of patients and the proportion of patients with severe hypoglycemia events, symptomatic hypoglycemia, and carbohydrate interventions due to hypoglycemia will be summarized descriptively. The number of events will also be summarized. The proportions will be analyzed by a Fisher's exact test, if data allow. The sample SAS code for the analysis involving the proportion of subjects that had a carbohydrate intervention due to hypoglycemia is included here:

```
.....  
Note: treatment = treatment group (1=Lilly glucagon, 2=ZP4207)  
carb = subject had a carbohydrate interventions due to  
hypoglycemia (Yes or No).  
.....  
proc freq ;  
tables treatment*carb / fisher ;  
run;  
.....
```

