2.1.2 Secondary Objective

The secondary objectives of this trial are:

- To measure glycemic regulation, including hypoglycemia exposure (percent of time spent with continuous glucose monitor [CGM] glucose < 60 mg/dL).
- To evaluate BP device reliability.
- To document the satisfaction of patients with the BP with the goal of optimizing the functionality and user interface of the BP.

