
1. Once the patient has been enrolled and eligibility has been established, the order of the treatment visits will be randomized in blocks of 2 patients.
 
2. In Part 1, each patient will participate in 2 treatment visits: 1 with the iPhone-based BP using ZP4207 and 1 with the iPhone-based BP using Lilly glucagon in a randomized order. In Part 2, each patient will participate in 2 treatment visits: 1 with the iLet using ZP4207 and 1 with the iLet using Lilly glucagon in a randomized order. Up to 2 patients may participate in the trial per day.
 
3. The night before the visit, patients will place a Dexcom G4 CGM sensor in the abdominal skin and calibrate the sensor when prompted using the provided Nova StatStrip Xpress meter. Patients will be asked to arrive at the visit at least 1 hour in advance of the start of the BP having fasted since 12:00 AM the night before (treatment with simple carbohydrate of up to 30 g for a low is allowed). If the patient is not fasted, the visit will be rescheduled within the visit window. If BG is >250 mg/dL, the visit will be rescheduled within the visit window. If BG is <50 mg/dL, treatment with simple carbohydrate is allowed. If the patient experiences persistent hypoglycemia, the visit will be rescheduled within the visit window.
 
4. Visit 3 will take place at least 48 hours after screening (Visit 1) and no more than 30 days after screening (Visit 1).
 
5. There will be a 24-hour minimum washout between Visit 3 and Visit 4 and a maximum of 3 weeks between Visit 3 and Visit 4.
 
6. Visit 5 will take place 10 days ±3 days from Visit 4.
 
7. Visit 6 will take place 25 days ±4 days from Visit 4.
 
8. Height and physical examination will be measured at Visit 1 only.
 
9. Vital signs including body temperature and blood pressure will be obtained at visit start and visit end.
 
10. At visit start and visit end.
 
11. Urine HCG pregnancy test only for women of childbearing potential. The date of the last menstrual period in female patients will be obtained at Visit 1 only.
 
12. Test for FSH level only for postmenopausal women amenorrheic for less than 1 year.
 
13. If indicated by history.
 
14. Patients will be trained in the insertion and calibration of the Dexcom G4 sensor, diabetes management (e.g., basal insulin rate adjustment by insulin pump) during fasting prior to and between the treatment visits, and trial policies and procedures.
 
15. Collected at least hourly. If BG is <150 mg/dL, then sampling will be every 30 minutes. If BG is <100 mg/dL, then sampling will be every 20 minutes. If BG is <80 mg/dL, then sampling will be every 10 minutes.
 
16. Collected at least hourly. If BG is <150 mg/dL, more frequent samples for plasma ZP4207/glucagon may be drawn at the discretion of the Investigator.
 
17. Once the infusion sites have been placed but no drug has yet been administered.
 
18. Between approximately Hour 3 and Hour 4.
 
19. Between approximately Hour 6 and Hour 7.
 
20. Before the start of dosing.
 
ADA = anti-drug antibodies; BG = blood glucose; BP = bionic pancreas; CGM = continuous glucose monitor; ECG = electrocardiogram; FSH = follicle-stimulating hormone; HbA1c = hemoglobin A1c; HCG = human chorionic gonadotropin; VAS = visual analog scale.
						

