3.2.2.2 Glycemic Endpoints

All of the following metrics will be generated from the Dexcom G4 Platinum CGM data during each treatment visit:

- Fraction of time spent within each of the following glucose ranges:
 - <50 mg/dL
 - <60 mg/dL
 - <70 mg/dL
 - 70-120 mg/dL
 - 70-140 mg/dL
 - 70-180 mg/dL
 - >180 mg/dL
 - >250 mg/dL
 - >300 mg/dL
- Number of severe hypoglycemic events (patients unable to self-treat, requiring the assistance of another person)
- Number of episodes of symptomatic hypoglycemia
- Number of carbohydrate interventions for hypoglycemia
- Total grams of carbohydrates taken for hypoglycemia
- Mean CGM glucose

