4.7.1 Bionic Pancreas Function Endpoints

The plasma ZP4207/Lilly glucagon concentration will be summarized descriptively at each time point by treatment group (e.g. n, mean, SD, coefficient of variation [CV%], median, minimum, and maximum). Mean concentration will be plotted over time, by treatment group. Individual plasma concentration-time curves will be plotted by patient.

The analysis of BP function endpoints will be on an intention-to-treat basis. In cases where a treatment arm was not completed (and that arm was not repeated according to protocol criteria), available data from that arm will be used in the data analysis.

A paired t-test or the Wilcoxon signed rank test for comparison of means with normally or non-normally distributed residuals, respectively, will be used. The Shapiro-Wilk test will be used to determine the normality of the residuals for each comparison. The residuals will be obtained from an ANOVA model with treatment group as the fixed effect. If the p-value of the test is less than 0.001, the non-parametric method will be utilized to analyze the endpoint parameter. The sample SAS code for the paired t-test analysis involving the average percent of insulin dose amounts successfully delivered by the pump is included here:

```
.....  
Note: InsTrt1 = the average percent of insulin dose amount successfully  
delivered by the pump during treatment with Lilly glucagon.  
InsTrt2 = the average percent of insulin dose amount successfully  
delivered by the pump during treatment with ZP4207.  
.....  
proc ttest ;  
paired InsTrt1*InsTrt2;  
run;
```

In a secondary analysis, any period effect and any interaction between treatment and period will be looked for, although no such interaction is predicted for the efficacy outcomes. The efficacy outcomes will be analyzed using a mixed model including terms for treatment and period as fixed effects, an interaction term, and subject nested within sequence as a random effect. A patient must have a data value for both periods in order to be included in the analysis for the given parameter. The sample SAS code for this analysis is included here:

```
.....  
Note: Insulin = the average percent of insulin dose amounts successfully  
delivered by the pump  
subject = subject identification number.  
sequence = sequence order (1=glucagon/ZP4207, 2=ZP4207/glucagon).  
treatment = treatment group (1=Lilly glucagon, 2=ZP4207).  
period = analysis period number (1=Visit 3, 2=Visit 4).  
.....
```

```

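### Section 4.7.2 assigns the glycemic comparison to plasma glucose, not to the CGM metrics defined as endpoints, and gives no rule for summarising plasma samples drawn more often at low glucose

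*SAP*

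**What the plan says.** - **Objective (SAP 2.1.2).** Glycemic regulation is to be measured, and the one measure named is "percent of time spent with continuous glucose monitor [CGM] glucose < 60 mg/dL".
- **Endpoints (SAP 3.2.2.2).** The list opens with "All of the following metrics will be generated from the Dexcom G4 Platinum CGM data during each treatment visit". It contains time in nine glucose ranges, mean CGM glucose, and counts of hypoglycemia and carbohydrate interventions. Plasma glucose is not in it.
- **Analysis (SAP 4.7.2).** "Similar analysis, as described previously for the BP function endpoints, will be performed for the plasma glucose measurements". The only other test in that section is Fisher's exact test for the hypoglycemia and carbohydrate proportions.
- **What is carried over (SAP 4.7.1).** "A paired t-test or the Wilcoxon signed rank test for comparison of means with normally or non-normally distributed residuals, respectively, will be used". A mixed model with treatment, period and their interaction follows as a secondary analysis and is said to apply to efficacy outcomes. A patient needs a value in both periods to enter it.
- **General rule (SAP 4.7).** All secondary endpoint variables get descriptive statistics by treatment group and visit time point.
- **Plasma glucose sampling (SAP 3.1, Table 1, footnote 15).** At least hourly, every 30 minutes below 150 mg/dL, every 20 below 100, and "If BG is <80 mg/dL, then sampling will be every 10 minutes".
- **Drug concentration (footnote 16 and SAP 4.7.1).** Samples are at least hourly; below 150 mg/dL "more frequent samples for plasma ZP4207/glucagon may be drawn at the discretion of the Investigator". "The plasma ZP4207/Lilly glucagon concentration will be summarized descriptively at each time point by treatment group", and the means are plotted over time.

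**The concern.** The objective and the endpoint list agree on CGM, and the analysis section names a different measurement. A programmer who follows 4.7.2 as written would run the paired test and the mixed model on a variable that is not an endpoint. No stated comparison would be run on CGM time below 60 mg/dL.

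The replacement variable has its own difficulty, because the sampling frequency depends on the value being measured. The paired test needs one number per patient and treatment. The BP function endpoints of 4.7.1 already come as one average percentage per visit; a set of plasma samples does not. The SAP gives neither a time weighting nor a restriction to hourly draws, so the choice could be made after the data are seen. The obvious default, a plain mean of all samples, over-weights low glucose. Low-glucose exposure is also what a comparison of two glucagon products may change, so the error need not be equal in the two arms.

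**Working it through.** The SAP gives no power calculation, effect size or glucose distribution, so there is no figure of its own to reproduce. The check has two parts.

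**1. Which variable is compared**

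| Place in SAP | Variable |
|---|---|
| 2.1.2 objective | CGM time below 60 mg/dL |
| 3.2.2.2 endpoints | CGM time in nine ranges, mean CGM glucose, event counts |
| 4.7.2 paired test and mixed model | plasma glucose |
| 4.7.2 Fisher's test | hypoglycemia and carbohydrate proportions |

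The CGM time-in-range and mean-glucose metrics have no row of their own in 4.7.2.

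**2. What a plain mean of the plasma samples would estimate**

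Sampling rates r from footnote 15, per hour: 60/60 = 1 at 150 mg/dL or above; 60/30 = 2 for 100 to 149; 60/20 = 3 for 80 to 99; 60/10 = 6 below 80. The ratio of highest to lowest is 6, relative to the hourly minimum.

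With t the share of time in a band and m its mean glucose:

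- time-weighted mean = Σ t·m
- plain sample mean = Σ t·r·m / Σ t·r

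Direction: the second equals the first plus Cov(r, glucose) / mean(r). Under footnote 15, r never rises as glucose rises, so the covariance is zero or negative and the plain mean cannot be too high. This uses only the sampling schedule, followed at its stated rates.

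Size: this needs assumptions. Band means are taken as 190, 125, 90 and 65 mg/dL. Time shares, from the highest band to the lowest:

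| Assumed shares (%) | Time-weighted mean | Plain sample mean | Difference |
|---|---|---|---|
| 50, 40, 7, 3 | 153.25 | 225.6/1.69 = 133.5 | −19.8 |
| 40, 40, 12, 8 | 142.0 | 239.6/2.04 = 117.5 | −24.5 |
| 35, 35, 15, 15 | 133.5 | 253.0/2.40 = 105.4 | −28.1 |

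Worked for the middle row: Σ t·m = 76 + 50 + 10.8 + 5.2 = 142.0. Σ t·r = 0.40 + 0.80 + 0.36 + 0.48 = 2.04. Σ t·r·m = 76 + 100 + 32.4 + 31.2 = 239.6.

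Effect on the contrast between arms:

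- One arm as in the top row, the other as in the middle row: the true difference is 153.25 − 142.0 = 11.25 mg/dL; the plain means differ by 133.5 − 117.5 = 16.0.
- Two arms with the same time-weighted mean of 140.5 mg/dL, one with shares 30, 60, 8, 2 and the other with 40.3, 37.7, 10, 12: the plain means are 236.4/1.86 = 127.1 and 244.6/2.177 = 112.4. The difference of 14.7 mg/dL is produced by the sampling alone.
- Two arms with identical profiles: the error cancels in expectation.

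**The case against.** **Plasma glucose may be a loose label for the CGM metrics.** The sentence stands under the heading Glycemic Endpoints, and the mixed model in 4.7.1 is written for efficacy outcomes generally, which could include CGM. A reader might infer that the CGM endpoints go unanalysed, and the SAP does not support that. Section 4.7 gives them descriptive statistics, the mixed model may reach them, and the event endpoints have Fisher's test. The objective is also to measure, with no hypothesis stated. What remains is that 4.7.2 names a different, separately collected measurement and states no comparison for the CGM metrics.

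**The SAP does not plan a plain mean.** This is correct. A reader might infer that biased summaries are prescribed, but the text has no reduction rule at all, and summaries at the hourly time points would avoid the over-weighting. It also plans no share of plasma samples below a cut-off. Time in range is defined from CGM only, and the plasma schedule does not affect it. The bias is therefore conditional on a choice that the SAP leaves open.

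**Drug concentration is a different matter.** A reader might infer that off-hour concentration means come only from patients with low glucose. Footnote 16 does not support that: its trigger is 150 mg/dL, and the extra draws are discretionary. In the three profiles above, 50%, 60% and 65% of time lies below 150. Concentration is not a listed endpoint and is only summarised and plotted. The selection of patients at extra time points is real but minor.

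**Glycemia is secondary.** The primary endpoint is safety, compared qualitatively, and no formal sample size was calculated. This stands and limits the severity.

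**Conclusion.** The point holds as an inconsistency between the defined endpoints and the stated analysis. Sections 2.1.2 and 3.2.2.2 specify CGM, while 4.7.2 assigns the paired test and mixed model to plasma glucose. That part rests on the text alone.

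The missing rule for reducing plasma samples to one value per patient and treatment also rests on the text. If all samples were averaged plainly, the mean would be too low. The direction follows from footnote 15. The size, about 20 to 28 mg/dL, rests on assumed time shares and band means and would shrink if samples at higher glucose were drawn more often than the hourly minimum. The treatment contrast would be distorted only where the arms' glucose profiles differ.

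This should be fixed, but it does not threaten the trial's main conclusion, because the primary safety endpoint does not depend on 4.7.2.

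**What to change.** 1. In 4.7.2, name the CGM metrics of 3.2.2.2 (time in each range and mean CGM glucose) as the variables for the paired and mixed-model analyses, with CGM time below 60 mg/dL first.
2. If plasma glucose is kept, label it supportive and define one value per patient and visit. Use either a time-weighted mean (trapezoidal area divided by the time from first to last sample) or the mean of the scheduled hourly samples only, with a stated rule for which sample represents each hour.
3. As a minor point, base the mean drug-concentration tables and plots on the scheduled hourly samples. Keep the extra draws in the individual curves and listings.

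The cost is SAP wording and programming. All the data are already planned for collection. The only loss is that the extra concentration samples no longer enter the group means. The change is best made before the possible interim database lock after Part 1 (SAP 4.7.4), so that both parts are analysed by the same rule.

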3. TRIAL OVERVIEW

3.1 Overall Trial Design and Treatment Assignment

[figure not shown]
This is a Phase 2 single-center, open-label, 2-part, randomized cross-over trial in adult patients (≥ 18 years of age) with T1DM. Patients who already manage their T1DM using continuous subcutaneous (SC) insulin infusion pump therapy will be enrolled. The trial will assess the safety and efficacy of the BP, using either the iLet or the iPhone platform, using the glucagon analog

ZP4207 versus Lilly glucagon. In Part 1, up to 10 patients will participate in two 1-day treatment arms in random order (iPhone-based BP using ZP4207 and iPhone-based BP using Lilly glucagon) according to the randomization scheme. In Part 2, up to 10 new patients will participate in two 1-day treatment arms in random order (iLet using ZP4207 and iLet using Lilly glucagon) according to the randomization scheme. The BP will also administer insulin (insulin lispro, Lilly Humalog) using the same blood glucose (BG) control algorithm for all 4 treatment arms. The trial will be conducted at the Massachusetts General Hospital (MGH) Diabetes Center in Boston, MA. Up to 40 patients will be enrolled in this trial with the expectation that up to 10 patients will complete each part of the trial.

[figure not shown]
The overall trial design is displayed in Figure 1.

Figure 1. Trial Design Schematic

Part 1:

Part 2:

Patients can only participate in 1 part of the trial.
 ADA = anti-drug antibodies, BP = bionic pancreas.

Patients who have completed the Screening Visit and meet all of the inclusion and none of the exclusion criteria will be enrolled. The order of the treatment visits will be randomized in blocks of 2 patients.

The schedule of events for the trial is provided in Table 1.

Table 1. SCHEDULE OF PROCEDURES – PARTS 1 AND 2

Trial Visit	Visit 1 [1] Screening	Visit 2 Training	Visit 3 [2] [3] [4] [5] (1 st Treatment Visit)	Visit 4 [2] [3] [5] (2 nd Treatment Visit)	Visit 5 ADA Assessment Visit [6]	Visit 6 Follow-Up [7]
Informed consent	X					
Assess/confirm eligibility	X	X				
Demographics	X					
Medical, surgical, and social history; allergies	X					
Concomitant illness	X					
Concomitant medications	X	X	X	X	X	X
Height, weight, physical examination, and vital signs including body temperature and blood pressure [8]	X		X [9]	X [9]		
12-lead ECG	X		X [10]	X [10]		
Urine HCG pregnancy test and menstrual history [11]	X		X	X		
FSH [12]	X					

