4. STATISTICAL METHODOLOGY

4.1 Baseline, Endpoint, and Other Statistical Considerations

The clinical statistical analyses will be performed by Medpace.

Descriptive summary statistics including number (n), mean, median, standard deviation (SD), and range (minimum, maximum) for continuous variables (interquartile range [25th, 75th percentile] for non-parametric tests), and counts and percentages for categorical variables will be used to summarize data, as appropriate. Where appropriate, p-values will be reported. All statistical tests will be conducted using 2-sided tests with 5% significance level and 95% confidence interval, unless otherwise stated.

For all analyses, the 2 treatment arms from Part 1 (iPhone-based BP) will be compared, and the 2 treatment arms from Part 2 (iLet) will be compared. The analyses of Part 1 will be completely separate from the analyses of Part 2.

All data will be listed in patient-level data listings.

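### The hypoglycemia proportions are compared by Fisher's exact test, which treats the two visits of each cross-over patient as independent and ignores the pairing

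*SAP*

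**What the plan says.** SAP section 3.1 describes two cross-over parts: "In Part 1, up to 10 patients will participate in two 1-day treatment arms in random order", and "In Part 2, up to 10 new patients will participate in two 1-day treatment arms in random order". Note 2 to the schedule of procedures (Table 1) confirms one ZP4207 visit and one Lilly glucagon visit per patient. Section 4.1 compares the two arms within each part ("The analyses of Part 1 will be completely separate from the analyses of Part 2") and sets the level: "All statistical tests will be conducted using 2-sided tests with 5% significance level".

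For the proportions of patients with severe hypoglycemia, symptomatic hypoglycemia and carbohydrate intervention, section 4.7.2 says: "The proportions will be analyzed by a Fisher's exact test, if data allow". Its sample code is `proc freq` with "tables treatment*carb / fisher". The outcome is one yes/no value per patient and treatment ("carb = subject had a carbohydrate interventions due to"), and the code has no subject, period or sequence variable.

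For continuous endpoints, section 4.7.1 plans "A paired t-test or the Wilcoxon signed rank test for comparison of means", followed by a mixed model with a random subject effect. The SAP gives no paired method for binary data.

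**The concern.** Fisher's exact test compares two independent groups. Here the two rows of the table hold the same patients, so the independence assumption is false by design. The code leaves no room for another reading, and it conflicts with the paired treatment of the continuous endpoints in the preceding section.

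In a paired comparison, the evidence on the treatment difference lies in the discordant patients, those with the event on one drug but not on the other. Fisher's test cannot see them. It uses only the total with the event under each treatment. Two data sets with very different paired evidence can give the same p-value, and two with the same discordant split can give different ones. These are the only tests planned for the three proportions.

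**Working it through.** **Inputs.** Up to 10 patients per part, each with both treatments (section 3.1). Two-sided 5% (section 4.1). Parts analysed separately (section 4.1). Section 5 expects 20 to 24 patients randomized; if 24 split evenly (an assumption), there are 24/2 = 12 pairs per part. The SAP gives no event rates, within-patient correlation or power, so those below are assumptions. There is no planned figure to reproduce.

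**Notation.** Of n patients with both visits, *a* have the event on both drugs, *b* only on the first, *c* only on the second, and *d* on neither. The event totals are *a+b* and *a+c*.

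- Fisher uses the table [*a+b*, *n−a−b*; *a+c*, *n−a−c*], which depends only on the totals.
- Exact McNemar, with m = *b+c* and *b* > *c*: p = 2·P(X ≤ *c*), X ~ Binomial(m, ½).
- Mid-p McNemar (*b* ≠ *c*): exact p minus C(m, *c*)/2^m.

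**Step 1. Same totals, different pairing (n = 10, 8/10 versus 2/10).** Three values of *a* are possible.

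| *a* | *b*:*c* | Fisher | Exact McNemar | Mid-p McNemar |
|---|---|---|---|---|
| 2 | 6:0 | 0.023 | 2·1/64 = 0.031 | 0.031 − 1/64 = 0.016 |
| 1 | 7:1 | 0.023 | 2·9/256 = 0.070 | 0.070 − 8/256 = 0.039 |
| 0 | 8:2 | 0.023 | 2·56/1024 = 0.109 | 0.109 − 45/1024 = 0.065 |

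Fisher is significant in all three rows. Exact McNemar disagrees at 7:1 and 8:2. Mid-p disagrees only at 8:2.

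**Step 2. Same discordant split, different concordant patients (n = 10, 5:0).** Five patients are concordant, so *a* runs from 0 to 5.

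| *a* | Totals | Fisher |
|---|---|---|
| 0 or 5 | 5 v 0, or 10 v 5 | 0.033 |
| 1 or 4 | 6 v 1, or 9 v 4 | 0.057 |
| 2 or 3 | 7 v 2, or 8 v 3 | 0.070 |

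Exact McNemar is 2/32 = 0.0625 throughout, and mid-p is 0.0625 − 1/32 = 0.031. Against mid-p, Fisher misses the difference when one to four patients had the event on both drugs. Against exact McNemar, it is significant when none or all five did.

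**Step 3. Size.** For event rates p1, p2 and correlation ρ, P(event on both) = p1·p2 + ρ·√[p1(1−p1)p2(1−p2)]. The multinomial probabilities of all tables with p ≤ 0.05 are summed. Fisher's size under the null, event rate 0.5:

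| ρ | n = 10 | n = 12 |
|---|---|---|
| −0.3 | 0.029 | 0.047 |
| 0 | 0.013 | 0.023 |
| 0.3 | 0.003 | 0.007 |
| 0.5 | 0.0008 | 0.002 |

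At zero or positive correlation and n = 10, the largest Fisher size over event rates 0.1 to 0.9 was 1.3%. It passed 5% only at strongly negative correlation (8.3% at ρ = −0.9, event rate 0.5). Mid-p McNemar was at most 3.6% (n = 10) and 4.0% (n = 12) at rates 0.3 and 0.5 with ρ from −0.3 to 0.5.

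**Step 4. Power (assumed rates and ρ = 0.3).** For 70% versus 20%, P(both) = 0.14 + 0.3·√(0.21·0.16) = 0.195.

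| Scenario | Fisher | Exact McNemar | Mid-p McNemar |
|---|---|---|---|
| 70% v 20%, n = 10 | 40% | 38% | 61% |
| 70% v 20%, n = 12 | 62% | 60% | 79% |
| 70% v 30%, n = 10 | 20% | 18% | 36% |

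**The case against.** The best defence is that little depends on these p-values. They belong to three of many secondary endpoints, section 4.6 compares primary safety only qualitatively, section 5 makes no formal sample size calculation, and no decision rule uses them. Section 4.7.2 also summarizes patients and events descriptively, and section 4.1 lists all data by patient, so the discordant counts can be recovered. All of this stands and limits the severity. It does not make the test fit the design.

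The qualifier that the test is run if data allow makes it conditional but does not restore the pairing. Under section 4.7, available data from an uncompleted arm are used, so a patient with only one visit appears once; the fault concerns those with both visits.

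A further objection is that McNemar's test is not the only remedy and ignores period, whereas section 4.7.1 looks for period effects in the efficacy outcomes. That is fair. A Mainland-Gart or Prescott test, or description alone, would also be defensible.

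**Conclusion.** The point holds: the specified test assumes independent groups in a cross-over, and its p-value ignores the pairing. With 10 pairs, one Fisher value of 0.023 covers paired results from 0.031 to 0.109 (exact) or 0.016 to 0.065 (mid-p). One 5:0 split gives Fisher values from 0.033 to 0.070. These p-values assume only 10 patients with both visits.

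Three stronger readings are not supported:

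- **Fisher inflates false positives.** A reader might infer this from records being counted twice. At plausible within-patient correlations the test is conservative, and the excess appears only at strongly negative correlation, which is implausible for the same patient on two days.
- **Pairing by itself gains power.** At these sample sizes exact McNemar has slightly less power than Fisher in the scenarios tried. The gain comes from mid-p, under assumed rates and correlation.
- **The trial's main conclusion is at risk.** The primary assessment is descriptive safety, and nothing in the SAP turns on these tests.

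The section should be corrected, at the weight of a secondary-endpoint error.

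**What to change.** In section 4.7.2, replace Fisher's test with McNemar's test on one record per patient with both visits, cross-classifying the outcome on Lilly glucagon with the outcome on ZP4207. State that the mid-p value is the one reported. Report the discordant counts in each direction, and the paired difference in proportions with a 95% CI for paired data.

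The code must match the text. `tables carb_glucagon*carb_zp4207 / agree; exact mcnem;` sets up the right table, but as written it requests only the plain exact test. Add a step that subtracts the binomial probability of the observed discordant split when the two counts differ.

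The cost is one paragraph and a few lines of code before database lock. Patients with only one treatment visit leave the test but stay in the descriptive counts. The test does not adjust for period; if that matters to the team, a Mainland-Gart or Prescott test could be named instead.

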5. SAMPLE SIZE DETERMINATION

No formal sample size calculations were made. It is expected that between 20 and 24 patients will be randomized in the trial. The sample size is based on a clinical rather than statistical rationale. The sample size is considered adequate to address the primary trial objective of

exploring the safety of ZP4207 when used in the BP and with reference to Lilly glucagon used in the BP.

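### Section 4.7.2 names a test for the hypoglycemia event endpoints only on a per-patient Yes/No score, although section 3.2.2.2 defines those endpoints as counts and grams of carbohydrate

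*SAP*

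**What the plan says.** SAP section 3.2.2.2 lists the endpoints as quantities for each treatment visit. They include "Number of carbohydrate interventions for hypoglycemia", "Total grams of carbohydrates taken for hypoglycemia" and counts of severe and of symptomatic hypoglycemia.

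Section 4.7.2 summarizes how many patients, and what proportion, had each kind of event, and applies Fisher's exact test to the proportions if the data allow. The code note defines the tested variable as "carb = subject had a carbohydrate interventions due to" hypoglycemia, with values Yes or No. For the counts it says only: "The number of events will also be summarized". Grams of carbohydrate are not mentioned in 4.7.2; they are reached only by the general rule in 4.7 that secondary variables are described by treatment group.

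The paired t-test or Wilcoxon signed-rank analysis of 4.7.1 is carried into 4.7.2 for plasma glucose measurements. Event counts and grams are not named there.

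On size and level: "In Part 1, up to 10 patients will participate in two 1-day treatment arms in random order"; Part 2 has the same structure; "The analyses of Part 1 will be completely separate from the analyses of Part 2"; and "All statistical tests will be conducted using 2-sided tests with 5% significance level".

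**The concern.** No endpoint in this group has a named comparison on the scale on which it is defined. Once events are reduced to any/none, one intervention counts the same as five. If most patients need at least one intervention on both drugs, most are scored Yes/Yes, and the reported p-value can suggest no difference beside clearly different counts.

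This is separate from the fact that the Fisher code treats the two rows as independent groups although each patient appears in both. A paired test on the same Yes/No variable would discard the same information.

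At stake is secondary inference about how often patients needed carbohydrate or had symptoms on ZP4207 compared with Lilly glucagon. The primary safety conclusion is not affected.

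**Working it through.** **Inputs from the SAP.** Two-sided 5% level (4.1). Up to 10 patients per part, each treated in both arms (3.1). Parts analysed separately (4.1). On the total, section 5 says: "It is expected that between 20 and 24 patients will be randomized in the trial", that is 10 to 12 per part if split evenly; 10 is used below. The SAP has no power or sample size calculation, so there is no planned figure to reproduce.

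**Assumed, because the SAP gives no event rate.** Counts are Poisson with mean μ × g, where g is a patient effect shared by both arms (gamma, mean 1, squared CV c). No period effect is modelled.

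**Step 1: what Fisher's test can see with 10 per row.**
- All 10 patients have 5 interventions on one drug and 1 on the other: the table is 10/10 vs 10/10 and p = 1.0. On the counts, all 10 differences equal 4 in the same direction, and the exact paired sign-flip p is 2/2^10 = 2/1024 = 0.002.
- 10/10 vs 5/10: p = 2 × C(10,5)/C(20,5) = 2 × 252/15504 = 0.0325. By symmetry 5/10 vs 0/10 gives the same.
- 10/10 vs 6/10: p = 2 × C(10,4)/C(20,4) = 2 × 210/4845 = 0.0867. So from a full row, at least 5 patients must change category.

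**Step 2: probability of scoring Yes.** For c = 0 it is 1 − exp(−μ); for c > 0 it is 1 − (1 + cμ)^(−1/c). Example with c = 0.5: μ = 3 gives 1 − 2.5^(−2) = 0.840, and μ = 1 gives 1 − 1.5^(−2) = 0.556. A threefold difference in counts becomes 84% vs 56%.

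**Step 3: simulated rejection rates (%), 10 patients, 3,000 runs per row.**

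| Mean events per visit | c | P(Yes), two arms | Fisher, Yes/No | Exact paired test, Yes/No | Paired t, counts | Exact paired sign-flip, counts |
|---|---|---|---|---|---|---|
| 3 vs 1 | 0 | 0.950 / 0.632 | 19.4 | 8.4 | 82.8 | 75.5 |
| 3 vs 1 | 0.5 | 0.840 / 0.556 | 8.9 | 5.1 | 70.5 | 66.3 |
| 3 vs 1 | 1 | 0.750 / 0.500 | 4.1 | 3.3 | 57.4 | 56.8 |
| 2 vs 1 | 0 | 0.865 / 0.632 | 8.7 | 3.9 | 36.5 | 27.9 |
| 2 vs 1 | 0.5 | 0.750 / 0.556 | 3.2 | 1.9 | 30.8 | 23.7 |
| 2 vs 1 | 1 | 0.667 / 0.500 | 1.4 | 1.2 | 25.5 | 19.2 |
| 1 vs 0.5 | 0 | 0.632 / 0.393 | 8.0 | 6.3 | 20.7 | 11.7 |
| 1 vs 0.5 | 0.5 | 0.556 / 0.360 | 3.8 | 2.8 | 15.9 | 8.6 |
| 0.5 vs 0.25 | 0 | 0.393 / 0.221 | 4.1 | 2.3 | 9.0 | 3.0 |
| 0.5 vs 0.25 | 0.5 | 0.360 / 0.210 | 2.6 | 1.4 | 8.4 | 2.1 |
| 1 vs 1 (no effect) | 0 | 0.632 / 0.632 | 1.2 | 0.8 | 4.3 | 2.0 |

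A separate run with the signed-rank statistic, for c = 0 and 0.5, gave: at 3 vs 1, Fisher 10-18%, signed-rank 67-77%, paired t 71-82%; at 2 vs 1, 4-8%, 25-30% and 32-37%. The two runs agree within simulation error.

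**Step 4: why.** Among patients whose counts differ between arms, the Yes/No rule scores as ties about 52-56% at 3 vs 1 and 47-49% at 2 vs 1, but only 5-10% at 0.5 vs 0.25. The paired Yes/No test does no better than Fisher's, so correcting the pairing alone would not recover the loss. The no-effect row shows that the count tests do not gain power by exceeding the 5% level.

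**The case against.** The strongest case on the other side has four parts.

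- **Counts and grams are not dropped.** They are summarized by treatment group under 4.7 and 4.7.2, and describing rather than testing them is defensible with about 10 patients per part and no formal sample size. This stands as a limit on importance. It does not explain why a test is applied to a reduced version of the endpoints and none to the endpoints themselves.
- **The counts may already be modelled.** Section 4.7.1 sends efficacy outcomes to a mixed model without defining the term. The counts might be included, so the statement that Yes/No is the only tested scale is certain for 4.7.2 but not for the whole SAP. If they are meant to be included, the text should say so.
- **The loss depends on the event rate.** This stands in full. A reader might infer that most of the treatment contrast is always lost, or that nearly all patients score Yes in both arms. The SAP has no rate to support either. At a mean of 1, only 56-63% score Yes (c = 0.5 or 0), and with rare events almost nothing is lost. For severe hypoglycemia, where 0 or 1 event per patient is plausible, Yes/No is nearly equivalent to the count.
- **A paired count test is also weak at moderate effects.** True: at 2 vs 1 it misses the difference more often than it finds it. It is still several times more likely to find it than the planned test.

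A reader might also infer that the secondary objective on hypoglycemia exposure is undermined. It is not: section 2.1.2 specifies that exposure as percent of time with CGM glucose below 60 mg/dL, a separate endpoint in 3.2.2.2.

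**Conclusion.** The mismatch holds from the text alone: the endpoints are defined as counts and grams, and the only test that 4.7.2 names for the event endpoints is on any/none. Its cost is conditional. At assumed means of about 2 or more events per visit in the worse arm it is large: roughly 10-18% power against 67-82% at 3 vs 1, and 4-8% against 25-37% at 2 vs 1, with no or moderate between-patient variation (c = 0 or 0.5). Stronger variation (c = 1) lowers both sides, to 4% against 57% at 3 vs 1. At 0.5 vs 0.25 the choice hardly matters. These figures rest on 10 patients, Poisson counts, a shared patient effect and no period effect.

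The correction is worth making because it is cheap and draws on methods already in the SAP. It concerns secondary, exploratory results only.

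**What to change.** In 4.7.2, state that within each part the per-patient number of carbohydrate interventions, number of symptomatic episodes and total grams of carbohydrate are compared between arms by a paired analysis of within-patient differences, and that the within-patient difference is reported with a 95% confidence interval.

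Then choose one of two options and write it down:
- apply the rule of 4.7.1 as it stands. It uses the paired t-test unless the Shapiro-Wilk p-value is below 0.001; at assumed means of 2 vs 1, 3 vs 1 and 4 vs 2 it would select signed-rank in only about 1-17% of simulated trials; or
- name signed-rank as the pre-specified method for these three variables. This is a new choice and not what 4.7.1 already provides.

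Keep the any/none proportions, and severe events, as descriptive. State in 4.7.1 whether efficacy outcomes include these variables.

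Cost: a few lines of SAP text and further calls of a procedure already planned, with no new data. The downside is three additional comparisons per part, 3 × 2 = 6 in all, which should be reported as secondary and exploratory, without multiplicity control.
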